10.7.2 Follow-up Requirements for Early Withdrawal

Patients will continue to be assessed every three months with an MRI and history and physical exam which is our standard of care.

10.7.3 Replacement of Early Withdrawal(s)

We will accrue 40 patients and will not replace patients once the accrual process is through. We treat over 300 SRS patients a year and we estimate that we should be able to accrue to the study readily.

10.8 Study Assessments

10.8.1 Medical History

A thorough medical history and review of systems will be obtained by the NP/MD. Oncologic information will be updated each visit, such as: type and duration of systemic therapies and performance status. The HVLIT, MMSE, and FACT-BR will also be administered with each visit.

10.8.2 Physical Exam

Standard Physical exam including extensive neurology exam will be performed with each follow up visit.

10.8.3 Correlative Assessment

Not applicable

11 SAFETY MONITORING AND REPORTING

The PI is responsible for the identification and documentation of adverse events and serious adverse events, as defined below. At each study visit, the PI or designee must assess, through non-suggestive inquiries of the subject or evaluation of study assessments, whether an AE or SAE has occurred.

11.1.1 AEs of Special Interest

Patients will be evaluated throughout the study for toxicity. Patients will be assessed for all adverse events during treatment and post completion of RT. Adverse Events (AEs) that are deemed by the PI to be related to the SIMT SRS treatment will be collected and reported. Acute adverse events will be collected at the first post-SRS visit. This visit will occur approximately 4 weeks after the last fraction of SRS is delivered. While not all-inclusive, the list below indicates side effects that may be related to the treatment. In the largest trial examining SRS treatment to 5-10 multiple targets (n = 1194), grade I & 2 toxicity was seen in 5% and Grades 3-4 were seen in 3%, and grade 5 toxicity <1%.¹²

SRS Possible Side Effects

Likely:

Mild erythema in the treatment field
Nausea / vomiting
Headaches
Fatigue

Less likely:

Hair loss in the treatment field
Decreased mental abilities
Extremity weakness
Parathesias
Speech difficulties
Hydrocephalus
Radionecrosis
Seizures
Vision loss
Death

11.1.2 Reporting of AEs

For all adverse events deemed by the PI to be related to the SIMT SRS treatment, the information should be recorded in the patient's medical record and the Case Report Form or AE database for that patient. This should include a description of the event, its severity or toxicity grade, the relationship to the study treatment, and the intervention, outcome and sequelae of the event.

11.2 Serious Adverse Events

An AE is considered "serious" if in the opinion of the investigator it is one of the following outcomes:

- Fatal
- Life-threatening
- Constitutes a congenital anomaly or birth defect
- A medically significant condition (defined as an event that compromises subject safety or may require medical or surgical intervention to prevent one of the three outcomes above)
- Requires inpatient hospitalization or prolongation of existing hospitalization
- Results in persistent or significant incapacity or substantial disruption to conduct normal life functions

Any serious or unexpected event, which occurs to any patient in the course of their treatment on this study or within 30 days following cessation of treatment, is reported immediately to the Study Coordinator by [contact], within 24 hours of the clinician learning of its occurrence.

11.3 Safety Oversight Committee (SOC)

The Duke Cancer Institute SOC is responsible for annual data and safety monitoring of DUHS sponsor-investigator phase I and II, therapeutic interventional studies that do not have an independent Data Safety Monitoring Board (DSMB). The primary focus of the SOC is review of safety data, toxicities and new information that may affect subject safety or efficacy. Annual safety reviews include but may not be limited to review of safety data, enrollment status, stopping rules if applicable, accrual, toxicities, reference literature, and interim analyses as provided by the sponsor-investigator. The SOC in concert with the DCI Monitoring Team (see Section 12.1 for Monitoring Team description) oversees the conduct of DUHS cancer-related, sponsor-investigator greater-than-minimal-risk intervention studies that do not have an external monitoring plan, ensuring subject safety and that the protocol is conducted, recorded and reported in accordance with the protocol, standing operating procedures (SOPs), Good Clinical Practice (GCP), and applicable regulatory requirements. The DCI Safety Oversight Committee (SOC) will perform annual reviews on findings from the DCI Monitoring Team visit and additional safety and toxicity data submitted by the Principal Investigator.

11.4 External Data and Safety Monitoring Board (DSMB)

We do not have a potential conflict of interest.

12 QUALITY CONTROL AND QUALITY ASSURANCE

12.1 Monitoring

The Duke Cancer Institute (DCI) Monitoring Team will conduct monitoring visits to ensure subject safety and to ensure that the protocol is conducted, recorded, and reported in accordance with the protocol, standard operating procedures, good clinical practice, and applicable regulatory requirements. As specified in the DCI Data and Safety Monitoring Plan, the DCI Monitoring Team will conduct routine monitoring after the third subject is enrolled, followed by annual monitoring of 1 – 3 subjects until the study is closed to enrollment and subjects are no longer receiving study interventions that are more than minimal risk.

Additional monitoring may be prompted by findings from monitoring visits, unexpected frequency of serious and/or unexpected toxicities, or other concerns and may be initiated upon request of DUHS and DCI leadership, the DCI Cancer Protocol Committee, the Safety Oversight Committee (SOC), the sponsor, the Principal Investigator, or the IRB. All study documents must be made available upon request to the DCI Monitoring Team and other authorized regulatory authorities, including but not limited to the National Institute of Health, National Cancer Institute, and the FDA. Every reasonable effort will be made to maintain confidentiality during study monitoring.

12.2 Audits

The Duke School of Medicine Office of Audit, Risk and Compliance (OARC) may conduct confidential audits to evaluate compliance with the protocol and the principles of GCP. The PI agrees to allow the OARC auditor(s) direct access to all relevant documents and to allocate his/her time and the time of the study team to the OARC auditor(s) in order to discuss findings and any relevant issues.

OARC audits are designed to protect the rights and well-being of human research subjects. OARC audits may be routine or directed (for cause). Routine audits are selected based upon risk metrics generally geared towards high subject enrollment, studies with limited oversight or monitoring, Investigator initiated Investigational Drugs or Devices, federally-funded studies, high degree of risk (based upon adverse events, type of study, or vulnerable populations), Phase I studies, or studies that involve Medicare populations. Directed audits occur at the directive of the IRB or an authorized Institutional Official.

OARC audits examine research studies/clinical trials methodology, processes and systems to assess whether the research is conducted according to the protocol approved by the DUHS IRB. The primary purpose of the audit/review is to verify that the standards for safety of human subjects in clinical trials and the quality of data produced by the clinical trial research are met. The audit/review will serve as a quality assurance measure, internal to the institution. Additional goals of such audits are to detect both random and systemic errors occurring during the conduct of clinical research and to emphasize “best practices” in the research/clinical trials environment.

12.3 Data Management and Processing

12.3.1 Case Report Forms (CRFs)

The REDCap Database CRF (electronic) will be the primary data collection document for the study. The CRF will be updated in a timely manner following acquisition of new source data. Only approved study staff are permitted to make entries, changes, or corrections in the CRF.

An audit trail will be maintained automatically by the REDCap electronic CRF management system. Designated personnel will complete user training, as required or appropriate per regulations.

12.3.2 Data Management Procedures and Data Verification

Clinical research nurses, all investigators, and statisticians involved in the project will have access to REDCAP based on their specific roles in the protocol. The designated data manager will be managing the REDCAP database.

Completeness of entered data will be checked automatically by the eCRF system, and users will be alerted to the presence of data inconsistencies. Additionally, the data manager will cross-reference the data to verify accuracy. Missing or implausible data will be highlighted for the PI requiring appropriate responses (i.e. confirmation of data, correction of data, completion or confirmation that data is not available, etc.).

The database will be reviewed and discussed prior to database closure, and will be closed only after resolution of all remaining queries. An audit trail will be kept of all subsequent changes to the data.

12.3.3 Study Closure

Following completion of the studies, the PI will be responsible for ensuring the following activities:

- Data clarification and/or resolution
- Review of site study records for completeness
- Shipment of all remaining laboratory samples to the designated laboratories.

13 STATISTICAL METHODS AND DATA ANALYSIS

All statistical analysis will be performed under the direction of the statistician designated in key personnel. Any data analysis carried out independently by the investigator must be approved by the statistician before publication or presentation.

13.1 Analysis Sets

All patients who undergo SIMT SRS treatment will be included in both safety and efficacy analyses.

13.2 Patient Demographics and Other Baseline Characteristics

Socio-demographic and clinical characteristics of patients enrolled and treated on this study will be summarized. For categorical variables, frequencies and percentages will be provided. Means with standard deviations and medians/percentiles will summarize non-categorical variables. Included among the clinical variables that will be summarized will be diagnosis (i.e. site of primary disease), and size and location of brain metastases.

13.3 Treatments

A frequency distribution for the number and volume of brain metastases, as well as the total brain volume receiving 12 Gy or more (V_{12Gy}), will be generated. Details about concomitant treatment of the primary disease will also be summarized.

13.4 Primary Objective

The primary objective of this study is to assess the impact of using SIMT SRS for the treatment of patients with ≥ 4 brain metastases.

13.4.1 Variable

Though local control is of primary interest in this study, there is concern about the ability to differentiate between swelling due to radiation and disease progression without conducting a biopsy. The use of a biopsy to determine recurrence is not feasible given the number of brain metastases. Hence we focus on the survival of patients with brain metastases who are treated with SIMT SRS. The goal of the study is to confirm that use of SIMT SRS does not reduce the prognosis of patients.

The population of patients with brain metastases is a heterogeneous population with expected survival ranging between 3 and 25 months. We will use the expected survival defined by the diagnosis-specific GPA (Graded Prognostic Assessment) index to assess the efficacy of SIMT SRS.¹⁶ Specifically, for each patient we will determine whether the patient lives longer than expected based upon the GPA index. If the survival of patients treated with SIMT SRS is truly comparable to the survival of patients treated with currently available treatment regimens, then we would expect that approximately half of the patients would live longer than expected.

Hence, the primary endpoint of the study will be the proportion of patients who live longer than expected according to the diagnosis-specific GPA index.

13.4.2 Statistical Hypothesis, Model, and Method of Analysis

The goal of the study is to confirm that the use of SIMT SRS does not significantly reduce or compromise the prognosis of patients. Within each of 5 diagnosis groups (non-small cell lung cancer, melanoma, breast cancer, renal cell carcinoma, and GI cancer), various prognostic groups have been defined by Sperduto.¹⁶ Within each of these diagnosis-prognosis groups, an expected survival has been determined. It is hoped that the survival of patients treated with SIMT SRS is similar to or better than that seen among Sperduto's cohort. In other words, it is hoped that the survival with SIMT SRS is not inferior to that reported in the Sperduto paper.

With the expected proportion of patients living longer than expected to be 50%, a test of non-inferiority will be conducted. Details are provided in the section concerning sample size justification.

Additionally, the Kaplan-Meier estimator will be used to describe the survival of all patients treated with SIMT SRS. The survival of patients within diagnosis-specific subgroups will also be similarly described. Within the context of the Kaplan-Meier estimator, median survival, 6-month survival, and 12-month survival will be estimated. Survival is defined as the time between initiation of SIMT SRS and death, and will be censored at last follow-up if the patient remains alive.

13.4.3 Inferences

This study has been designed with the best historical data currently available to assess the efficacy of SIMT SRS in a single-arm study. However, this benchmark is imperfect, and does not reflect the possible impact of rapidly emerging novel therapeutics, including immunotherapies, that target the primary disease of these patients. In addition, this benchmark does not reflect the few

patients we may have with recurrent brain metastases as the GPA scoring was developed from a database that included patients who completed brain treatment within 2 months of the diagnosis of brain metastases. If a better benchmark data becomes available during the conduct of this study, the design of this single-arm study may be modified.

Though a decision-rule is provided in section 13.8 to test the non-inferiority of SIMT SRS treatment relative to the Sperduto GPA-based benchmark, other factors will be considered in determining whether further usage of SIMT SRS is reasonable. Two important issues that will factor into this decision-making include: technical feasibility of administering SIMT SRS, and clinical factors such as neurologic control and local control.

13.5 Secondary Objectives

The key secondary objective is to describe the time to local recurrence. Other secondary objectives focus on the time to distant recurrence, time to neurologic death, and the prevalence of significant adverse events.

13.5.1 Key Secondary Objective

The time until local brain recurrence will be calculated as the time between initiation of SIMT SRS and local recurrence of brain metastases. The time to local brain recurrence will be censored at the time of last follow-up if the patient remains alive without local recurrence, or will be censored at death if the patient dies without local recurrence of brain metastases. A Kaplan-Meier estimator will be used to describe the time until local recurrence. Within the context of Kaplan-Meier curve, an estimate of the proportion of patients without local brain recurrence one year after SIMT SRS treatment will be generated. The time until local brain recurrence will also be described within diagnosis-specific subgroups.

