5 OBJECTIVES AND ENDPOINTS

	Objective	Endpoint	Analysis
Primary	Assess the impact of using SIMT SRS for the treatment of brain metastases on survival	Proportion of patients who live longer than predicted according to the Graded Prognostic Assessment (GPA) score	See Section 13.4
Key Secondary	Describe the time to local brain recurrence	Proportion of patients that experience local brain recurrence within 1 year of SIMT SRS treatment.	See Section 13.5.1
Other Secondary	Describe the time to distant brain recurrence	Proportion of patients that experience a new brain metastasis at a site different from the original brain metastasis site 1 year after SIMT SRS treatment	See Section 13.5.2
Other Secondary	Describe the time to death due to neurological causes	Proportion of patients who are dead within 1 year of SIMT SRS treatment due to neurologic reasons	See Section 13.5.2
Other Secondary	Describe the prevalence of significant adverse events	Proportion of patients who experience grade 3, 4, or 5 neurologic adverse events attributable to SIMT SRS	See Section 13.5.2
Key Exploratory	Describe changes over time in neurocognition	Mean changes from baseline in subscales of the Trailmaking instruments and the HLVT	See Section 13.6.1
Key Exploratory	Describe changes over time in quality of life	Mean changes from baseline in subscales of the FACT-Brain instrument	See Section 13.6.1
Other Exploratory	Quantify treatment set up and dosimetric data for this treatment technique	Mean length of time to set-up and treat patient, Volume of brain exposed to 12Gy, Mean PTV dose, Total volume of all brain metastases, conformity index, maximum dose	See Section 13.6.2
Other Exploratory	Describe the rate of salvage therapy	The proportion of patients who receive salvage treatment after failing SIMT SRS	See Section 13.6.2
Other Exploratory	Describe prevalence of radionecrosis at the SRS site	Proportion of patients with radionecrosis at the SRS site; the proportion of lesions showing radionecrosis	See Section 13.6.2
Other Exploratory	Describe length and intensity of steroid usage post-SRS	Descriptive statistics	See Section 13.6.2

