13.5.2 Other Secondary Objectives

The time until distant brain recurrence will be calculated as the time between initiation of SIMT SRS and distant recurrence of brain metastases. The time to distant brain recurrence will be censored at the time of last follow-up if the patient remains alive without distant recurrence, or will be censored at death if the patient dies without distant recurrence of brain metastases. A Kaplan-Meier estimator will be used to describe the time until distant recurrence. An estimate of the proportion of patients without distance recurrence one year after SIMT SRS treatment will be generated. The time until distant brain recurrence will also be described within diagnosis-specific subgroups.

Time to neurologic death is defined as the time between initiation of SIMT SRS and death due to neurologic causes. If a patient remains alive or dies for reasons unrelated to neurologic disease, the time to neurologic death will be censored at the time of last follow-up or death not due to neurologic causes. Analyses similar to other “time to an event” outcomes will be conducted including the generation of Kaplan-Meier curves.

The proportion of patients who experience grade 3 or worse neurologic toxicity attributable to SIMT SRS will be summarized. In addition, adverse events experienced by protocol subjects will also be summarized in several other forms to satisfy scientific and monitoring needs, as well as various regulatory reporting needs (e.g. DCI SOC, and ClinicalTrials.gov). The frequency of adverse events that are possibly, probably, or definitely related to protocol treatment will be tabulated by the maximum grade for each type of adverse event.

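### The one-year local recurrence endpoint is defined as a proportion of patients, but 13.5.1 reads it from a Kaplan-Meier curve that censors deaths, so recurrence is overstated and local control looks worse than the endpoint defined

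*Combined protocol and SAP*

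**What the plan says.** **Endpoints (section 5).** The key secondary endpoint is "Proportion of patients that experience local brain recurrence within 1 year of SIMT SRS treatment". Two other secondary endpoints have the same form: "Proportion of patients that experience a new brain metastasis at a site different from the original brain metastasis site", assessed at one year, and "Proportion of patients who are dead within 1 year of SIMT SRS treatment due to neurologic reasons".

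**Local recurrence (13.5.1).** Follow-up ends at last contact for living recurrence-free patients, or it "will be censored at death if the patient dies without local recurrence of brain metastases". The text then ties the one-year figure to the Kaplan-Meier curve: "an estimate of the proportion of patients without local brain recurrence one year after SIMT SRS treatment will be generated".

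**Distant recurrence (13.5.2).** Time "will be censored at death if the patient dies without distant recurrence of brain metastases". A Kaplan-Meier estimator is named, and the next sentence reads "An estimate of the proportion of patients without distance recurrence one year after SIMT SRS treatment will be generated". That sentence does not itself mention the curve.

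**Neurologic death (13.5.2).** Here "the time to neurologic death will be censored at the time of last follow-up or death not due to neurologic causes", with similar analyses that include Kaplan-Meier curves. No one-year read-off is stated; it is implied only by section 5.

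**How recurrence is found.** Sections 3.3 and 10 define recurrence by MRI, planned every three months in year 1. Section 10 allows a scan to be skipped for clinical decline, and 10.5 makes imaging depend on clinical indication.

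The documents mention no competing-risk or cumulative-incidence method.

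**The concern.** A patient who dies at month 4 without recurrence has not had a recurrence within one year. For a proportion of patients, that person counts in the denominator as a non-event. Kaplan-Meier with death censored instead treats that person as still able to recur later, at the same rate as those who remain. The complement of the curve therefore estimates recurrence in a hypothetical setting without deaths, and only if death and recurrence are independent.

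Deaths will be frequent. Section 13.4.1 expects survival between 3 and 25 months, so many deaths fall inside the one-year window. A figure labelled as a proportion of patients would be too high for MRI-detected recurrence, by an amount that depends on survival. Diagnosis-specific subgroups with different survival would be distorted unequally. The figures also have a use: 13.4.3 lists neurologic and local control among the factors in deciding on further use of SIMT SRS.

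**Working it through.** The plan states no expected rate for these endpoints, so it has no figure of its own to reproduce.

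**Direction, without a hazard model.** At each recurrence time, let d be the number recurring and n the number at risk. Both estimators add up (d/n) × (a survival factor just before that time). For Aalen-Johansen the factor is the probability of being alive and recurrence-free. For one minus Kaplan-Meier it is the recurrence-free curve with deaths removed. The second factor is never smaller, and it is larger once any competing death has occurred. So one minus Kaplan-Meier is never below the cumulative incidence, and it is strictly above once a competing death precedes a later event.

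**Inputs for size**
- Survival of 60% at six months in an earlier single-isocenter study (section 3.2).
- One-year local control of 83% (section 4.2), from 26 patients with median follow-up 3.3 months. Its unit (patient or lesion) and estimator are not given; it is treated here as a per-patient Kaplan-Meier value.
- Appendix A medians of 3.0 and 25.3 months, as extreme single-stratum values.
- Assumption: constant, independent hazards.

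**Hazards per year**
- Death: d = −ln(0.60)/0.5 = 1.0217, giving a median of 8.1 months and one-year mortality of 64.0%.
- Recurrence: l = −ln(0.83) = 0.1863.

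**Recurrence seen at once**
- One minus Kaplan-Meier = 1 − exp(−l) = 17.0%.
- Cumulative incidence = l/(l+d) × [1 − exp(−(l+d))] = 0.1863/1.2080 × (1 − 0.2988) = 10.8%.
- Ratio 1.57, or 6.8 against 4.3 of 40 patients.

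**Three-monthly MRI, none missed**
- The chance that recurrence arises in each quarter, q, is 0.0455, 0.0434, 0.0415, 0.0396.
- Survival to scans at 3, 6, 9, 12 months is 0.775, 0.600, 0.465, 0.360.
- Detected proportion = sum of products = 0.0353 + 0.0261 + 0.0193 + 0.0143 = 9.5%.
- Kaplan-Meier still gives 17.0%, because each step is estimated only among survivors.
- The gap is 7.5 points, about 3 of 40 patients.

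**Scans missed before death.** Suppose each scan is done only if death comes more than m months later. Write S_D for survival, t_k for the k-th scan time, and q_k for the chance that recurrence arises in the quarter ending at t_k. Detected proportion = sum of q_k × S_D(t_k+m). The Kaplan-Meier hazard at t_k is q_k × S_D(t_k+m) / [S_D(t_k) − sum over j<k of q_j × S_D(max(t_j+m, t_k))]. Local recurrence, in percent:

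| Median survival | Scans missed | One minus KM | Detected (Aalen-Johansen) | Underlying |
|---|---|---|---|---|
| 3.0 mo | none | 17.00 | 4.13 | 5.97 |
| 3.0 mo | last 3 mo | 8.80 | 2.06 | 5.97 |
| 3.0 mo | last 5 mo | 5.54 | 1.30 | 5.97 |
| 8.1 mo | none | 17.00 | 9.48 | 10.82 |
| 8.1 mo | last 3 mo | 13.37 | 7.35 | 10.82 |
| 8.1 mo | last 5 mo | 11.31 | 6.20 | 10.82 |
| 25.3 mo | none | 17.00 | 13.97 | 14.56 |
| 25.3 mo | last 3 mo | 15.74 | 12.87 | 14.56 |
| 25.3 mo | last 5 mo | 14.93 | 12.18 | 14.56 |

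Kaplan-Meier is above the detected proportion in every row. Where scans are missed, it is closer than Aalen-Johansen to underlying recurrence. The same holds for distant recurrence at an assumed 50% net risk (l = ln 2), shown as KM/detected/underlying at the three medians:
- 3 months missed: 28.2/6.7/19.4, 40.9/22.5/33.2, 47.0/38.3/43.4.
- 5 months missed: 17.7/4.2/19.4, 34.9/18.9/33.2, 44.7/36.3/43.4.

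**Neurologic death.** With an assumed share s of deaths, one minus Kaplan-Meier = 1 − exp(−s·d) and cumulative incidence = s × (1 − exp(−d)). At s = 0.1, 0.3, 0.5 this gives 9.7% against 6.4%, 26.4% against 19.2%, and 40.0% against 32.0%.

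**Sampling error.** The exact 95% interval for 4 of 40 is 2.8% to 23.7%, which contains both 9.5% and 17.0%.

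**The case against.** **Kaplan-Meier suits an objective about time to recurrence, and published local-control rates may be of the same kind.** This stands as a reason to keep the curve, not as a reason to call its complement a proportion of patients.

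**Cumulative incidence is a poor measure of lesion control.** This also stands. With the same recurrence hazard and three-monthly MRI, it is 4.1% at a 3.0-month median and 14.0% at 25.3 months. A lower value can simply mean earlier death.

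**With missed scans, Aalen-Johansen is further from the truth.** Correct in all 12 missed-scan settings above. The overstatement is relative to MRI-detected recurrence, which is how sections 3.3 and 10 define the event. It is not established against every underlying recurrence.

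**The endpoints are descriptive, and the gap is smaller than the noise.** True, but the gap is systematic and sampling error does not remove it.

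A reader might infer more than the documents support:
- *That the plan flatters the treatment.* The error runs the other way: recurrence looks more frequent.
- *That all three endpoints are misread explicitly.* Only local recurrence is tied to the curve in words.
- *That 13.1 settles the matter by including all treated patients.* Kaplan-Meier also includes them all; the mismatch comes from section 5 and the censoring rule.
- *That threefold or fourfold overstatement is expected.* Those ratios come from the 3.0-month median of a single prognostic stratum, not from a cohort median.

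**Conclusion.** The mismatch is real and should be fixed. For local recurrence it is explicit: section 5 asks for a proportion of patients, and 13.5.1 delivers the complement of a net risk. Distant recurrence shares the problem on the natural reading of 13.5.2, and neurologic death does so if the figure implied by section 5 is read from its curve.

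The direction needs no hazard assumption: one minus Kaplan-Meier is too high for the MRI-detected proportion once competing deaths precede later events. The size is illustrative. At the survival and local-control rates the protocol cites, it is 17.0% against 10.8% or 9.5%, with a larger gap for shorter survival and a smaller one for longer survival. This rests on constant independent hazards and on an 83% figure of unknown unit and estimator. The distant and neurologic-death figures rest on assumed rates.

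The consequence is limited to how these secondary results are labelled and read. No threshold depends on them, and the survival decision rule is unaffected.

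**What to change.** 1. In 13.5.1 and 13.5.2, estimate the one-year proportions by the Aalen-Johansen cumulative incidence with confidence intervals. The competing event is death without the recurrence in question, or non-neurologic death. State that recurrence means MRI-detected recurrence.
2. Report Kaplan-Meier beside it as a labelled cause-specific summary, for the time-to-event objective and the literature comparison in 3.3. Say that a lower cumulative incidence is not to be read as better lesion control.
3. State as a limitation that scans missed before death (sections 10 and 10.5) make cumulative incidence understate underlying recurrence, and that Kaplan-Meier may then lie closer to it.
4. State whether local recurrence is still recorded after distant progression. Section 10.7.1 says patients who progress in the brain are followed only for survival, while 10.7.2 continues three-monthly MRI after withdrawal; the two must be reconciled. If local recording did stop at distant recurrence (assumed 50% net risk), the 10.8% would become 0.1863/1.9011 × [1 − exp(−1.9011)] = 8.3%.
5. At minimum, reword section 5 and 13.5 so that the Kaplan-Meier value is called a net risk, not a proportion of patients.

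The estimator change costs a few sentences and standard software, with no new data. The one-year figures become less directly comparable with published Kaplan-Meier rates, which the retained curve covers.
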